## 7.9. Qualitative interviews with patient and non-patient participants

We will conduct in-depth phone interviews with randomly selected 15 patients and 5 PCP participants with highest number of enrolled patients in the study. The Reach, Effectiveness, Adoption, Implementation and Maintenance (RE-AIM) framework will be used to guide the evaluation questions and examine the effectiveness of the intervention and implementation outcomes.

We will ask patients and providers to describe any barriers to LCS completion (for patients) and ordering (for providers) and describe their experience with use of various components of the intervention, as well as feedback on what they liked and disliked about the intervention, and what they would change to make it more helpful or engaging. Participants will be recruited via phone by the study coordinator, and interviews will be conducted on the phone, video conference or in person. We expect that patient interviews take 30 minutes, and provider interviews take 20 minutes. Interview participants will receive a \$40 gift card.

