## 1. PROTOCOL SYNOPSIS

Study Number	UCI 23-107
Study Title	Empowering patients' Lung Cancer Screening uptake (Empower LCS)
Development Phase	II
Funding Source(s)	Anti-Cancer Challenge Pilot Award
Operational Changes during the COVID-19 Pandemic	N/A
Sources of Study Drugs	N/A
Number and Identity of Study Sites	University of California Irvine Health
Study Rationale	Utilization of lung cancer screening (LCS) using Low Dose CT (LDCT) among those eligible is low. We are assessing feasibility of a multi-level intervention to improve lung cancer screening uptake.
Study Design	Single arm longitudinal study
Study Objectives	
 
1. Assess feasibility of our multi-level intervention in increasing patients' LCS knowledge, having a LDCT ordered, and patients' receipt of LCS with LDCT.
 
2. Assess LCS-eligible patients' and their providers' perceptions and barriers towards LCS.
 
3. Describe patients' & providers' experience with the intervention using a mixed-methods approach.
 

Planned and Maximum Sample Size	70 patient participants (English, Spanish, and Vietnamese speaking), and between 20-40 non-patient participants.
Duration of Study Participation	
Patient participants: 6 months. Up to 15 patients will be asked to participate in a 30-min interview after 6 months completion of the study.
 
Non-patient participants: One time. 5 non-patient participants will be asked to participate in a 30-min interview within 3 months of last patient enrollment.

Indication(s) Under Study	Patients eligible for lung cancer screening
Inclusion Criteria	
 
1. Aged 50- 80 years of age.
 

	
 
2. Be able to Speak English, Spanish, or Vietnamese
 
3. Must have a primary care provider
 
4. Meeting the LCS eligibility criteria based on self-reported smoking history (for UCI and non-UCI Health patients) as well as documented in EMR (for UCI Health patients) and confirmed prior to enrollment
 

Exclusion Criteria	
 
1. No prior history of lung cancer
 
2. No chest CT for any reason in the last 12 months based on self-report (for UCI and non-UCI Health patients) and UCI EMR (for UCI Health patients)
 
3. No history of Alzheimer's disease or dementia
 

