**G. Qualitative Interview**

15 patients will be randomly selected to undergo a 30-minute interview.

5 providers with highest number of enrolled patients in the study will undergo a 30-minute interview

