There are several barriers to LCS. **Provider barriers** includes the failure of the electronic medical record (EMR) to notify providers of eligible patients (most common), patient refusal, perceived high false-positive rate leading to unnecessary procedures, provider time constraints, and patients' lack of insurance coverage. Identifying eligible patients through EMR is often challenging as smoking pack-year data is either not complete or discordant (92.6% in one study) with patients' self-reported data obtained during patient-provider shared decision making conversations regarding LCS. This results in lack of trust of the primary care providers (PCP) to use EMR data for such purposes. **Patients' barriers** to LCS includes concerns regarding insurance coverage and co-pay for both screening and treatment (if diagnosed with cancer), access to convenient care, fear of a positive screening result or radiation exposure, and lack of understanding that lung cancer correlates with smoking history. Prior research assessing perceptions and barriers towards LCS and interventions to address barriers among diverse non-white and non-English-speaking population is limited. Interventions addressing LCS knowledge barriers have shown an increase in patients' knowledge or decisional certainty, but were not sufficient to increase receipt of LCS. On the other hand, interventions involving direct patient outreach (e.g., reminders to call and schedule LCS) or patient navigators addressing multiple barriers were more successful in increasing LCS uptake.

**Our proposed intervention**, informed by the Health Belief Model, is a multi-level intervention including: (1) PCP notifications of patients' LCS eligibility (addressing provider time constraints and barrier in identifying eligible patients); (2) patients' education (addressing knowledge barriers); (3) patients' referral to financial navigation resources (addressing health-related social risks); and (4) patients' reminder to discuss LCS during PCP visit. We propose to assess perceptions and barriers towards LCS and test our intervention among 0 English-, Spanish- and Vietnamese-speaking LCS-eligible patients with a scheduled PCP visit at any of UCI primary care clinics including FQHC or at non-UCI Health clinics in the next five months.

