##### 5.2. Overall Study Design

We will conduct a single arm longitudinal clinical trial of 70 LCS-eligible patients with a PCP appointment at UCI health within five **months** after enrollment. All patients will complete a baseline survey to assess their perceptions and barriers towards LCS and will receive a multi-level intervention. All patients will complete a survey at 6 months post-enrollment to assess changes in perceptions and knowledge, receipt of an order for LDCT or completion of LDCT, and experience with intervention. All primary care providers of enrolled patients will be sent a survey 3 months after last patient enrollment to assess providers' barriers to order LCS. We will interview randomly selected up to 15 patients and 5 PCP participants with highest enrolled patients in the study, who consent to be interviewed to assess experience with the intervention.

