## 10. STATISTICAL METHODS

### 10.1. Planned and Maximum Sample Size

A sample size of 70 patients is feasible given the limits of the study timeline and budget and will allow us to characterize key patient variables.

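### Interviewees are chosen at random with no strata or minimum by language, so a small Spanish- or Vietnamese-speaking group could go uninterviewed

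*Combined protocol and SAP*

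**What the plan says.** The selection rule for patient interviews appears in three places, and all three make it random.

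- Section 7.9: "We will conduct in-depth phone interviews with randomly selected 15 patients".
- Figure 1, step G: "15 patients will be randomly selected to undergo a 30-minute interview".
- Section 5.2: "We will interview randomly selected up to 15 patients". The same sentence adds the qualifier "who consent to be interviewed to assess experience with the intervention", so 15 is a maximum and the pool is best read as those who agree to be interviewed.

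None of the three mentions language, strata or a quota. The Synopsis describes the sample as "70 patient participants (English, Spanish, and Vietnamese speaking" with no target for each language. Section 10.1 justifies the total on practical grounds: "A sample size of 70 patients is feasible given the limits of the study timeline and budget".

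The three languages are nevertheless central to the study. Section 3 says that prior research on barriers and on "interventions to address barriers among diverse non-white and non-English-speaking population is limited". Sections 7.1, 7.3, 7.5 and 7.6 provide for outreach, coordinators, surveys and education material in the patient's language. Section 10.4 plans translation of the interviews, so interviews in other languages are expected.

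**The concern.** Effort is spent on recruiting Spanish and Vietnamese speakers, but nothing carries that effort through to the interviews. Section 7.1 itself notes that lacking an email address or not answering email is common among non-English-speaking patients, so small groups are plausible. The outreach it plans in response serves enrollment only. A random draw of 15 can then contain nobody, or a single person, from one language.

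At stake is part of the second secondary objective, the mixed-methods description of experience with the intervention. Under Section 7.9 the interviews are where patients describe in depth their barriers to completing screening, what they liked and disliked, and what they would change. If no one from a language group is interviewed, later analysis cannot supply that material.

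**Working it through.** The documents give no calculation for the interview sample, so there is no figure to reproduce. The check asks how often the stated rule would miss a language group.

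**Inputs**
- Patients enrolled: N = 70 (Synopsis, Section 5.4).
- Interviews: n = 15 (Section 7.9). This is the maximum under Section 5.2.
- Size of one language group among the 70: K. The documents do not give it. The values 5, 7, 10, 14, 20 and 23 are assumptions that run from a small group to about one third of the sample.
- Draw: without replacement and unstratified. No section uses the word simple; this is inferred from the absence of any strata.

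**Formulas**
- P(no interviewee from the group) = C(N−K, n) / C(N, n).
- P(at most one) = P(none) + K × C(N−K, n−1) / C(N, n).
- Expected interviewees from the group = nK/N.
- P(Spanish or Vietnamese missing, or both), equal groups of K = 2 × P(none; K) − P(none; 2K).

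**Example, K = 5.** C(65,15)/C(70,15) = (55×54×53×52×51)/(70×69×68×67×66) = 0.287. Expected interviewees = 15×5/70 = 1.07.

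**Results, 15 drawn from 70**

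| K (assumed) | Expected | None | At most one | Spanish or Vietnamese missing (K each) |
|---|---|---|---|---|
| 5 | 1.07 | 28.7% | 71.0% | 50.1% |
| 7 | 1.50 | 16.9% | 53.2% | 31.6% |
| 10 | 2.14 | 7.4% | 31.4% | 14.4% |
| 14 | 3.00 | 2.2%–2.3% | 13.5% | 4.5% |
| 20 | 4.29 | 0.3% | 2.9% | 0.6% |
| 23 | 4.93 | 0.1% | 1.2% | 0.2% |

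(The K = 14 entry is 0.0225 before rounding.)

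**Effect of non-consent.** Suppose 20% decline evenly across languages and the 15 are drawn from the 56 who agree (0.8 × 70). A group of 5 becomes 4 of 56, and P(none) is 27.6% against 28.7%. A group of 10 becomes 8 of 56, and P(none) is 6.7% against 7.4%. Even refusal that is made good therefore leaves the risk about the same.

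**Effect of fewer interviews.** If refusals are not replaced and only 12 of 70 are interviewed, a group of 5 is missed 37.9% of the time. With 10 of 70, a group of 7 is missed 32.2% of the time.

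**The case against.** The strongest objection is that the risk depends on an unknown language mix, and that recruitment leans toward the groups in question. Figure 1 and Section 7.1 direct flyers, clinics and media at Spanish and Vietnamese speakers. With groups of 14 or more, the chance of missing a given one is about 2% or less. This stands as a limit on size: a group of 5 is a pessimistic case, not a forecast. It does not supply a safeguard, because no enrollment minimum is set.

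A reader might infer that the objective would be left with no data on experience for a missed group. The documents do not support that. Section 7.7 surveys all patients on their experience with the intervention at 6 months, and Table 2 lists both survey and interview as sources. Only interview depth would be lost.

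A reader might also infer that refusal to be interviewed necessarily makes matters worse. It does so only if refusal is concentrated in the small group or refusals are not replaced.

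Two further points are fair. No objective is specific to a language, and random selection protects against staff choosing favorable interviewees; drawing at random within language keeps that protection. Also, Table 1 places each interview within 30 days of the patient's survey, so selection is rolling and language totals might not be known in time. This is largely answered by the timeline. Table 2 starts provider surveys 9 months after first enrollment, and Section 7.8 sends them 3 months after last enrollment, which implies about 9 − 3 = 6 months of enrollment. Patient interviews follow the 6-month survey, so the totals should be nearly known when they begin. The inference is approximate, because Table 1 words the provider survey as falling within 3 months of last enrollment.

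**Conclusion.** The point holds as a minor design improvement. The plan selects up to 15 consenting patients at random with nothing to secure coverage by language, although evidence in non-English-speaking patients is part of the reason for the study. Assuming 15 drawn from 70, a group of 5, 7, 10 or 20 has a 29%, 17%, 7% or 0.3% chance of no interviewee. If the three groups are about equal, the chance of missing either non-English group is about 0.2%. These figures rest on assumed group sizes and an unstratified draw. The consequence is confined to in-depth interview data under one secondary objective. The primary endpoint, an LDCT order within 6 months, is not affected. The documents do not support saying that a language group will be left out, only that nothing prevents it.

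**What to change.** In Sections 7.9 and 5.2 and in Figure 1, state that patient interviewees are selected at random within language, with a minimum for each non-English group. An example is at least 3 to 5 Spanish and 3 to 5 Vietnamese speakers, or all who consent if there are fewer. Fill the remaining places at random from all other consenting patients, and replace a refusal from the same language group. The number of interviews stays at 15, and a language is then missed only if none of its patients agrees.

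The change is cheap but not free. With 5 patients in each non-English group, the current rule expects 15×10/70 = 2.1 non-English interviews; with 10 in each, 15×20/70 = 4.3. Minimums of 3 and 3 bring this to at least 6, and minimums of 5 and 5 to 10. That means more bilingual interviewing and translation in a study sized by its budget, although Section 7.1 already has a bilingual team and Section 10.4 already plans translation. The interview sample would no longer be proportional to enrollment, which thematic analysis does not need.

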## 8. EFFICACY ASSESSMENTS

Primary end point is order of LDCT within 6 months after enrollment assessed with self-reported surveys (for UCI-Health and non-UCI health patients) and EMR data extraction (for non-UCI Health patients). Remainder of outcomes is show in Table 2.

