### 6.2. Exclusion Criteria

The following patients will not be eligible for participation in the study:

No prior history of lung cancer

No chest CT for any reason in the last 12 months based on self-report (for UCI-Health and non-UCI Health patients) and UCI EMR (for UCI-Health patients)

No history of Alzheimer's disease or dementia

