## 7. STUDY PROCEDURES

### 7.1. Pre-Screening

*UCI Health Patients:*

UCI clinical data warehouse will be inquired every week for a list of patients and their contact information, who are 50-80 years old, speaking English, Spanish or Vietnamese, and have a primary care provider, who are current or former smokers or have an unknown smoking history in EMR, and have no history of lung cancer, Alzheimer's disease or dementia, and have not received a chest CT or LDCT in the last 12 months. We will further inquire from primary care providers about their potentially eligible patients. EMR will also manually be reviewed to assess eligibility and generate an additional list for recruitment. We will take a note of patients with primary care appointment in next 5 months so that we have in person outreach.

We will send an email outreach with the study information, an option to opt out if not interested, and a short 2-min REDCap survey to verify LCS eligibility if interested in participating. For non-English speaking patients, the email outreach and survey will be sent in their preferred language. The survey includes questions on smoking history, prior history of lung cancer, and prior receipt of chest CT in the last 12 months.

To ensure our sample size is representative of population, we plan to have phone outreach, text message outreach, in person clinic visits to directly recruit participants, or mailing surveys (by bilingual research team) to patients who do not have an email address or do not respond to the email outreach, a common condition among non-English speaking patients.

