#### 7.5. Baseline Survey

Patients will be asked to complete a 15-min survey either on the phone or online via REDCap based on preference. This survey includes validated measures utilizing the Health Belief Model to assess perceived risk of getting lung cancer, benefits and barriers to LCS, and self-efficacy for LCS, prior receipt of any screening exam, overall willingness to undergo LCS with LDCT, and engage in receiving LCS educational information. We will further screen for health-related social risks such as financial hardship, difficulties in paying for food, transportation, and housing instability as a barrier to receipt of LCS, and query on demographics, insurance, health literacy, zip code (to assess neighborhood socioeconomic status), and presence of other comorbidities and healthy behaviors. Participants with completed survey will be sent a \$15 gift card. Survey materials will be available in English, Spanish, and Vietnamese.

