## 7.7. Patient Follow-up

Patients will be surveyed 6 months after enrollment to assess self-reported LCS discussion with PCP, provider order of LDCT, and patients' receipt of LDCT. We will also extract these from EMR only for UC-Health patients. Patients will be queried on LCS perceived risks, benefits, barriers, and self-efficacy, experience with intervention including educational material, reminders, and self-referral to PAF if PAF brochure was received.

Surveys will be completed online (REDCap), on the phone or paper (mailed with a pre-stamped pre-addressed envelope) based on patient's preference. Patients with completed survey will receive a \$15 gift card.

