**Table 2 . Study Outcomes, Measures and co-variates**

Efficacy Outcomes		
LDCT order for LCS	6 mo	Survey and EMR
Receipt of LDCT for LCS	6 mo	Survey &EMR
Pt and PCP LCS discussion	6 mo	
Pt perceived risks, benefit, barriers, and self-efficacy using LCS health belief mode 	Baseline & 6 mo	Survey
Process Evaluation Outcomes		
Rate of concordance of EMR and self-report smoking hx	Baseline	Survey& EMR
Showing up to PCP visit	6 mo	
Self-referral to PAF	6 mo	Survey
Pt and provider experience with intervention components	6 mo	Survey& interview
Provider perceived barriers and knowledge of LCS	Beginning 9 mo after first pt enrollment	Survey
Covariates		
Sociodemographics, insurance, neighborhood deprivation index, health literacy, comorbidities	Baseline	Survey
Financial worry  and health-related social risks 	Baseline & 6mo	Survey

- Any mention of ER is only for UCI Health patients.

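### No planned source identifies LDCT orders already open at enrollment, so self-report may count them as events, and how the EMR extraction treats them is undefined

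*Combined protocol and SAP*

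**What the plan says.** **Endpoint.** Section 8: "Primary end point is order of LDCT within 6 months after enrollment". In Table 2, the row "LDCT order for LCS" has a 6-month time point and no baseline one.

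**Sources.** Section 7.7: "Patients will be surveyed 6 months after enrollment to assess self-reported LCS discussion with PCP, provider order of LDCT". It then adds: "We will also extract these from EMR only for UC-Health patients". The synopsis and the footnote to Table 2 (which prints ER, evidently for EMR) agree that EMR data are for UCI Health patients. Section 8 prints the reverse, "EMR data extraction (for non-UCI Health patients", and has to be reconciled with the other three places.

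**Checks before the intervention.** All of them concern scans or exams received:
- Section 6.2 (exclusion): "No chest CT for any reason in the last 12 months based on self-report", with a matching EMR check for UCI patients.
- Section 7.1 (data-warehouse query): patients who "have not received a chest CT or LDCT in the last 12 months". The 2-minute survey in the same section also asks about chest CT received.
- Section 7.5 (baseline survey): "prior receipt of any screening exam".

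**Analysis.** Section 10.4 reports the proportion with an LDCT order descriptively. It has no rule for an order placed before enrollment, for a renewed order, or for disagreement between survey and EMR.

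**The concern.** The endpoint is tied to a window that starts at enrollment, but nothing records whether an order was already waiting when the window opened. Such patients are plausible. Section 7.6 says usual care already flags eligibility to the provider when the smoking history is complete, and Section 3 lists barriers (cost, access, fear of the result) that can leave an ordered scan undone.

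The study has a single arm, so no control group carries the same error and cancels it. The proportion with an order is itself the primary result. An order that came before the intervention could be credited to it. Where self-report is the only source, the study's own records would not reveal this afterwards.

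**Working it through.** **No figure to reproduce.** Section 10.1 justifies 70 patients by timeline and budget. The documents give no target order rate, precision goal or open-order rate.

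**Step 1. How a patient with an open order is counted.** Take a patient whose LDCT was ordered before enrollment and not yet done.

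| Rule | Counted as | Consequence |
|---|---|---|
| 6-month self-report, answered yes because an order exists | event | a pre-intervention order enters the numerator |
| EMR, any active order | event | same |
| EMR, only orders dated after enrollment | no event, unless renewed in the window | correct under the written definition, but the patient stays in the denominator and is less likely to get a new order |

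The documents do not say which EMR rule applies, and they do not show the wording of the 6-month survey item.

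**Step 2. Worst-case bounds.** Let q be the share with an open order at enrollment and p the order rate in the rest. Assume that every open order is reported as yes and that none is renewed. Both q and p are assumptions.

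- Self-report, or EMR counting any active order: q + (1 - q)p. Shift from p: +q(1 - p).
- EMR restricted to post-enrollment dates: (1 - q)p. Shift from p: -qp.

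With p = 40%:

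| q | patients of 70 | self-report | shift | date-restricted EMR | shift |
|---|---|---|---|---|---|
| 3% | 2.1 | 0.03 + 0.97 × 0.40 = 41.8% | +1.8 | 0.97 × 0.40 = 38.8% | -1.2 |
| 5% | 3.5 | 0.05 + 0.95 × 0.40 = 43.0% | +3.0 | 0.95 × 0.40 = 38.0% | -2.0 |
| 10% | 7 | 0.10 + 0.90 × 0.40 = 46.0% | +6.0 | 0.90 × 0.40 = 36.0% | -4.0 |
| 15% | 10.5 | 0.15 + 0.85 × 0.40 = 49.0% | +9.0 | 0.85 × 0.40 = 34.0% | -6.0 |

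**Step 3. Dependence on p.** Hold q at 10% (7 of 70). At p = 12.8%, the only background rate in the protocol (Section 3, for receipt rather than orders), the shifts are +0.10 × 0.872 = +8.7 and -0.10 × 0.128 = -1.3 points. At p = 50% they are +5.0 and -5.0 points. The upward error is larger when the true rate is low.

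**Step 4. Scale against sampling error, and precision cost of the fix.** The 95% half-width is 1.96 × √(p(1 - p)/n). At p = 40% and n = 70 it is 1.96 × √(0.24/70) = 11.5 points. At p = 30% it is 10.7 points with n = 70 and 11.3 points with n = 63, that is, if 7 patients leave the denominator.

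**The case against.** The strongest reply is that a date-restricted EMR rule makes no error. The endpoint is an order after enrollment, so a patient whose only order came earlier is rightly a no. For UCI patients, order dates would also show who had an open order, so they could be listed separately at analysis without a new baseline question. This stands. A reader might infer that these patients are misclassified whichever source is used, or that EMR data are shown to be biased down. The documents support neither: under a dated rule the fault lies in who is in the denominator, and whether the rule is dated is not stated.

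Other points that stand, in whole or in part:
- The 6-month item may carry a time window, and Section 7.5 only summarizes the baseline survey. So self-report may count these orders; it is not certain to.
- The intervention prompts both provider and patient, so an open order could be renewed within the window. That would be a true event.
- A reader might infer that survey and EMR results will differ by 3 to 15 points. That gap is q(1 - p) + qp = q. It restates the assumed open-order rate and is not a finding.
- A reader might infer that UCI and non-UCI results cannot be compared. All patients answer the 6-month survey, so a like-for-like comparison exists. The distortion arises only if EMR results in one group are set against survey results in the other.
- A reader might infer that receipt will exceed orders. Under the dated rule with p = 40% and all open orders completed, completion of new orders would have to exceed 1 - q/((1 - q)p): 92% at q = 3%, 87% at 5%, 56% at 15%. This is possible, but too conditional to rely on.
- The analysis is descriptive, with no test or threshold, so no formal decision changes. This limits the severity. It does not remove the problem, because the proportion is the primary result.

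**Conclusion.** The gap is real and the plan should close it. As written, a patient with an open order can enroll. If that patient is outside UCI Health, no planned source can later tell the earlier order from one placed after enrollment. The likely direction in self-report is upward, in favor of the intervention. In the EMR it depends on a rule that has not been written.

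The size is unknown. The bounds of +1.8 to +9 points and -1.2 to -6 points rest on an assumed 40% order rate, open-order rates of 3% to 15%, every open order reported as yes, and none renewed. Relaxing either of the last two assumptions shrinks them. At the low end they are small against a half-width of about 11.5 points. Unlike sampling error, though, they would not shrink with more patients.

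Reading non-UCI patients as self-report only follows the synopsis, Section 7.7 and Table 2 against Section 8 as printed.

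**What to change.** - **Section 7.1.** Add one item to the 2-minute survey for all patients: *LDCT for screening already ordered and not yet done*. For UCI patients, also extract open-order status and order date from the EMR.
- **Section 8.** State that only orders placed after enrollment count, in both sources, and word the 6-month survey item to match. Report the primary proportion in patients with no open order at enrollment. Report those with an open order on a separate line, and keep them for the receipt, discussion and survey outcomes. Give the proportion in all 70 as a sensitivity result, since keeping everyone in one denominator is also defensible.
- **Section 8, data sources.** Reconcile the EMR assignment with the synopsis, Section 7.7 and Table 2.

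The cost is one extra question, one EMR extraction and a slightly smaller primary denominator. With 7 patients removed, the half-width grows by 0.6 points at an assumed 30% order rate. One limit remains: a non-UCI patient who does not know of an open order will not report it, so the item reduces the problem there without removing it.
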